2.1.5. Secondary Outcome Measures: Neonatal

- Neonatal intensive care unit (NICU) admission
- Transient tachypnea of the newborn (TTS)
- Respiratory distress syndrome (RDS)
- Meconium aspiration syndrome
- Culture proven sepsis
- Seizures
- Composite of adverse neonatal outcomes:
 - Apgar score ≤ 7 at 5 mins
 - Umbilical cord pH < 7.1
 - Neonatal injury: brachial plexus injury, fracture
 - Perinatal death

2.2. Design Summary

This is a comparative-effectiveness, open-label, randomized controlled trial of induction of labor with transcervical Foley balloon and vaginal misoprostol versus misoprostol alone in nulliparous obese pregnant women and Bishop score ≤ 6 .

2.3. Inclusion Criteria

- Nulliparous women aged 18 or above
- BMI ≥ 30 at the time of labor induction
- Singleton gestation
- Cephalic presentation (includes successful external cephalic version)
- Intact fetal membranes
- Unfavorable cervix (Bishop score of ≤ 6)
- Gestational age ≥ 32 weeks

2.4. Exclusion Criteria

- Patient not candidate for IOL with misoprostol as deemed by the treating physician
- Multiple gestation
- Major fetal anomalies
- Fetal demise

2.5. Recruitment and Feasibility

Recruitment will occur at the Labor and Delivery units at Memorial-Hermann Hospital – Texas Medical Center, Lyndon B. Johnson General Hospital and Kern Medical, Bakersfield, CA.

2.6. Randomization

Randomization will be achieved by computer-generated random sequences. Permuted block randomization will be performed, stratified by center. Women will be randomized to either Foley balloon plus misoprostol or misoprostol alone as the method of choice for IOL. Enrollment number and assignments will be placed in opaque sealed envelopes. Envelopes will be kept secured in a locked office and will be accessible only by the research personnel.

2.7. Intervention and Procedures

[figure not shown]
Nulliparous pregnant women at ≥ 32 weeks' gestation admitted to labor and delivery for IOL and who meet the inclusion and exclusion criteria will be approached by the research staff (Figure 1). Group 1 will be composed of women allocated to the Foley balloon plus misoprostol. These women will receive vaginal misoprostol per standard protocol at 25 micrograms every 4 hours. In addition, a 26 Fr-Foley balloon catheter will be inserted by routine clinical standards. The Foley will be inserted through the internal cervical os, filled with 60 mL of normal saline, and then pulled snugly against the internal os. The catheter of the Foley will be taped to the patient's inner thigh under gentle traction. If the Foley is unable to be placed, the patient will be reexamined in 1 hour and placement will be reattempted if Bishop's score is still 6 or less by the healthcare provider. When the Foley balloon had fallen out or had to be removed because 12 hours have passed since insertion as per protocol, further management of labor will be left at the discretion of the labor team.

Group 2 will be composed of women allocated to vaginal misoprostol-only. These women will receive 25 micrograms of misoprostol per vagina every 4 hours. This time interval has been shown to be more effective than different time intervals in a Cochrane review²⁰. Once the cervix becomes favorable (Bishop score > 6), misoprostol administration will be discontinued. Similarly, further management will be left at the discretion of the labor team.

In both groups, if IV oxytocin is indicated, it will be withheld until 4 hours after the last dose of misoprostol to prevent uterine hyperstimulation. Other aspects of labor management will be similar for both groups, including continuous electronic fetal monitoring with external Doppler device or fetal scalp electrode. Uterine contraction assessment will be performed with either an external tocodynamometer or an intrauterine pressure catheter.

Participant data including demographic characteristics, medical and obstetric history, labor course and outcomes will be collected by a dedicated research nurse.

Figure 1. Flow Diagram – CROWN Trial

[figure not shown]

2.8. Safety Assessment

2.8.1 Risks Associated with Vaginal Misoprostol of Foley Balloon for Labor Induction

[figure not shown]
There is biologic plausibility that a Foley balloon catheter for cervical ripening may be associated with an increased rate of chorioamnionitis because it represents a foreign body in the lower uterine segment and could potentially facilitate an ascending infection. However, a systematic review by Fox et.al.²¹ (Figure 2) and a Cochrane review from Jozwiak et.al.^{22,23} (Figure 3) concluded that the rates of chorioamnionitis were comparable for the Foley balloon and misoprostol when used independently. Carbone et. al.¹² also reported no differences in the rates of chorioamnionitis when the Foley balloon was used concomitantly with misoprostol versus misoprostol alone.

Figure 2. Impact of Misoprostol vs Foley Balloon on Risk of Chorioamnionitis

Adapted from Fox NS, Saltzman DH, Roman AS, Klausner CK, Moshier E, Rebarber A. Intravaginal misoprostol versus Foley catheter for labour induction: a meta-analysis. *BJOG Int J Obstet Gynaecol* 2011;118:647–54.
 Abbreviations: CI, confidence interval; LCI, lower confidence interval; UCI, upper confidence interval

Figure 3. Impact of Prostaglandins vs Balloon catheter on Risk of Chorioamnionitis

Adapted from Jozwiak M, Bloemenkamp KWM, Kelly AJ, Mol BWJ, Irion O, Bouvain M. Mechanical methods for induction of labour. *Cochrane Database Syst Rev* 2012;3:CD001233.
 Abbreviations: CI, confidence interval

Tachysystole is a common complication of misoprostol administration for cervical ripening, and tachysystole with FHRT changes is more frequent among women receiving misoprostol than among those treated with mechanical devices, alternate prostaglandin compounds or oxytocin^{20,24,25}. However, the frequency of uterine tachysystole with FHRT changes was lower when a Foley balloon catheter was added to misoprostol than when misoprostol alone was used^{22,26}, purportedly due to the reduced need for additional doses of vaginal misoprostol. The combination could provide extra benefits to patients who are at higher risk of fetal hypoxemia, such as those with sickle cell disease, oligohydramnios, fetal growth restriction or other chronic diseases for which the use of misoprostol is not considered contraindicated^{27,28}.

2.8.2. Specification of Safety Parameters

Both of the interventions proposed are done in routine clinical care and have been tested in prior trials. Choriamnionitis is in fact a risk but is comparable to standard of care. The medications/interventions are not new in pregnancy and misoprostol is known to not be teratogenic in the third trimester. Therefore, the establishment of a safety data monitoring board is not necessary. The principal investigator (PI) and mentor will monitor the progress of study and determine the safety parameters.

2.8.3. Management of Adverse Events

Any adverse events will be reported to the Committee for the Protection of Human Subjects (CPHS). Due to the use of medications that have been used in pregnancy in the past, there is no increased anticipation of severe adverse events.

2.8.4. Procedures in the Event of Abnormal Clinical Findings

In the event of an abnormal clinical finding, the health care provider caring for the participant will be notified to allow treatment in the usual clinical manner.

2.9. Statistical Considerations

2.9.1. Sample Size

Assuming a cesarean delivery rate of 53% at Memorial Herman Hospital among nulliparous obese women who underwent IOL in 2012 at ≥ 32 weeks and met our inclusion criteria, 250 women (125 women per group) would be required for 80% power to detect a 33% cesarean delivery rate reduction between the 2 groups using a two-tailed t test and α of 0.05 (Table 2). Interim analysis after 50% enrollment will be performed in order to determine if the risk of adverse events discussed in the secondary outcomes is increased in one arm relative to the other arm.

Table 2. Proposed Sample Size

| % decrease in CD rate | Power (%) | | |
|-----------------------|-----------|-----|-----|
| | 80 | 85 | 90 |
| 33 | 250 | 270 | 316 |
| 40 | 172 | 196 | 228 |

| | | | |
|----|-----|-----|-----|
| 50 | 100 | 114 | 134 |
|----|-----|-----|-----|

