2.9.2. Statistical Tests

An intent-to-treat analysis will be conducted. Selected baseline characteristics and outcome measures will be compared using the independent t test for continuous variables and the X^2 or Fisher's exact test for categorical variables as appropriate. Mann-Whitney U test will be used for non-parametric comparisons. Tests with a p-value < 0.05 will be considered significant.

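### Does the inconsistent 33% row of Table 2 undermine the planned sample size of 250?

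*Combined protocol and SAP*

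**What the plan says.** Section 2.9.1 sets out the sizing in one sentence: "Assuming a cesarean delivery rate of 53% at Memorial Herman Hospital" in the control arm, "250 women (125 women per group) would be required for 80% power to detect a 33% cesarean delivery rate reduction", "using a two-tailed t test and α of 0.05".

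Table 2, headed "Proposed Sample Size", gives total numbers by percentage "decrease in CD rate" for 80%, 85% and 90% power:

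- 33% decrease: 250, 270, 316
- 40% decrease: 172, 196, 228
- 50% decrease: 100, 114, 134

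The intervention-arm rate behind each row is not printed, and no formula is named. Section 2.1.3 makes the cesarean delivery rate the primary outcome. Section 2.9.2 keeps the t test for continuous variables and prescribes a chi-square or Fisher's "exact test for categorical variables as appropriate".

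**The concern.** With the effect and alpha fixed, the required number rises by a nearly constant factor as power rises: about 1.14 from 80% to 85%, and 1.34 from 80% to 90%. The 40% row (1.14 and 1.33) and the 50% row (1.14 and 1.34) behave this way. The 33% row gives 270/250 = 1.08 and 316/250 = 1.26, which no single effect size produces.

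Table 2 is the only justification of the trial's size, and the faulty row is the one the trial uses. A reader would infer that 20 more women buy 85% power, when the formula asks for 288 − 252 = 36. Naming a t test for a yes/no outcome adds doubt about which test was planned for. If the same error reached the 250, the trial would be underpowered for its primary comparison.

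**Working it through.** **Inputs (section 2.9.1).** Control rate p1 = 0.53; relative reduction 33%; two-sided alpha 0.05 (z = 1.960); equal groups. The reduction has to be relative: an absolute fall of 33 points (53% to 20%) would need only 66 women. So p2 = 0.53 × 0.67 = 0.3551.

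**Formula.** Number per group for two proportions, pooled variance under the null:

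n = [1.960 × √(2p̄(1 − p̄)) + z_power × √(p1(1 − p1) + p2(1 − p2))]² / (p1 − p2)², with p̄ = (p1 + p2)/2.

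**The plan's own figure first.** p̄ = 0.44255, √(2p̄(1 − p̄)) = 0.7024, √(p1(1 − p1) + p2(1 − p2)) = 0.6915, (p1 − p2)² = 0.03059. For 80% power (z = 0.842):

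n = (1.960 × 0.7024 + 0.842 × 0.6915)² / 0.03059 = 125.4 per group.

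That is 250 in total if rounded to the nearest woman per group, or 252 if rounded up. The planned number reproduces.

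**The rest of the 33% row at p2 = 0.3551.**

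| Power | Computed total (rounded up) | Table 2 | Power at the Table 2 number |
|---|---|---|---|
| 80% | 252 | 250 | 79.9% |
| 85% | 288 | 270 | 82.8% |
| 90% | 336 | 316 | 88.3% |

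Other formulas do not rescue 270 and 316. Unpooled variance gives 246/282/330, and a t test with average variance gives 248/284/332. Reading 33% as exactly one third (p2 = 0.3533) gives 246/282/328 pooled and 242/276/322 unpooled.

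**Where 270 and 316 come from.** Solving the formula for p2 in each cell gives 0.3548 for 250, 0.3500 for 270 and 0.3501 for 316. At p2 = 0.35, n per group is 118.19, 135.00 and 157.73, so the totals rounded to nearest are 236/270/316. The last two match exactly.

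**Do the other rows point to a deeper fault?** With unrounded rates they seem to use different formulas: the 50% row (p2 = 0.265) equals the unpooled result, 100/114/134, while the 40% row (p2 = 0.318) lies within 2 of the pooled result, 170/194/226. With whole-percent rates one pooled formula covers both:

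- p2 = 0.32: n = 85.80, 97.94, 114.36; totals 172/196/228, identical to Table 2.
- p2 = 0.26: n = 50.26, 57.29, 66.79; totals 100/114/134, identical to Table 2.

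So rates of 35%, 32% and 26%, one formula and rounding to nearest reproduce eight of the nine cells. The 250 is the exception: it fits the unrounded 35.5%, and on the table's apparent basis it would be 236.

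**Power of the planned 250 on either basis.** 79.9% at 53% versus 35.5%; 82.2% at 53% versus 35.0%.

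**The case for a change.** The strongest case for a change is that the table fails on its own terms. The 1.08 ratio needs no view on effect size or formula, and the table's other two rows show what the ratio should be. Two of the three cells in the row the trial relies on overstate power, the sizing sentence names a test that section 2.9.2 reserves for continuous variables, and putting it right would cost a few cells and one phrase.

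The arithmetic in this stands. The further claim that the table mixes formulas, and so should be recomputed throughout, does not: the 40% and 50% rows reproduce exactly under one pooled formula with whole-percent rates. That reading is an inference, because the plan does not print those rates and the rounding is not uniform (26.5% becomes 26%, and 35% comes from 35.3% more naturally than from 35.5%). It is still simpler than supposing two formulas, and it fits better. The two effect sizes in the 33% row then differ by only half a percentage point in the intervention rate.

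The t-test wording is a slip with little numerical effect: 248 by the t test against 252 by the pooled formula, either side of the 250 chosen. The choice of analysis test is settled in section 2.9.2.

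**Conclusion.** The 33% row is inconsistent, and the inconsistency is clerical. At a true 33% reduction the 85% and 90% cells overstate power by 2.2 points (85 − 82.8) and 1.7 points (90 − 88.3). Neither cell was chosen. The figure that governs the trial, 250 women for 80% power, is within 2 women of the recomputed 252 and has 79.9% to 82.2% power under either intervention rate that the table implies. Tidying the row and the test name would leave enrolment, the primary analysis and the possible conclusions as they are, so no change to the plan is called for.

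This rests on reading the 33% as a relative reduction, on equal groups, on a two-sided alpha of 0.05 and on the plan's 53% control rate. That rate comes from one hospital in 2012. It is taken as given here.

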A number of randomized trials have compared the use of the Foley balloon in combination with misoprostol, against misoprostol alone for labor induction (Table 1). Carbone et.al.¹² randomized 123 women undergoing IOL with singleton pregnancies at \geq 24 weeks' gestation with unfavorable cervix (Bishop score \leq 6) to Foley balloon plus vaginal misoprostol or vaginal misoprostol alone. The mean induction-to-delivery time was shorter with the combined approach when compared to vaginal misoprostol alone (15.3 ± 6.5 compared with 18.3 ± 8.7 hours, difference -3.1 hours, 95% CI -5.9 to -0.30). No differences were noted in labor complications, CD rates (37.3 vs 26.2 %, P = 0.90) or neonatal outcomes, likely due to small sample size. These findings contrast with the results by Kashanian et.al.¹³ and Lanka et.al.¹⁴, who did not find such an association. However, the results from Kashanian et.al. must be interpreted with caution given potential biases due to unclear random sequence generation, high allocation concealment and selective reporting. In a recent meta-analysis of eight studies and 1153 patients by Chen et.al.¹⁵, the use of Foley balloon plus misoprostol was associated with a significant reduction in the mean time to delivery when compared to misoprostol alone (mean difference -2.36 hours, 95% CI -4.07 to -0.66; P = 0.007). Differences in cesarean delivery rates, however, remain elusive likely due to the small sample sizes of the trials included.

To our knowledge no studies have compared the effects of these interventions in

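### Is the interim safety look at 125 women asked to do something the protocol's own background says a trial of that size cannot do?

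*Combined protocol and SAP*

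**What the plan says.** Section 2.9.1 (Sample Size) sets the total at 250 women and adds a single interim analysis after half are enrolled. Its stated purpose is "in order to determine if the risk of adverse events discussed in the secondary outcomes is increased in one arm" compared with the other. It gives no event rates, power, threshold or decision rule for that look. The only significance criterion anywhere is the general p < 0.05 in section 2.9.2.

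Section 1 (Background) describes an earlier trial that "randomized 123 women undergoing IOL with singleton pregnancies" to Foley balloon plus vaginal misoprostol or vaginal misoprostol alone. It reports: "No differences were noted in labor complications", then names cesarean rates, and ends the sentence "or neonatal outcomes, likely due to small sample size".

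Section 2.8.1 returns to the same trial, which "also reported no differences in the rates of chorioamnionitis when the Foley balloon was used concomitantly with misoprostol versus misoprostol alone". The reviews cited just before it concluded that "rates of chorioamnionitis were comparable for the Foley balloon and misoprostol when used independently". Section 2.8.2 states "Choriamnionitis is in fact a risk but is comparable to standard of care" and, together with routine use and prior testing of both interventions, concludes that "the establishment of a safety data monitoring board is not necessary". The principal investigator and mentor monitor the study, and section 2.8.3 sends any adverse event to the institutional committee.

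**The concern.** The two comparisons differ by two women, 125 against 123, and concern the same pair of treatments. Taken together, the sections seem to read a null at about 62 women per arm in three ways: probably a product of small size (section 1), supportive of comparability (2.8.1 and 2.8.2), and enough to settle whether harm is increased (2.9.1).

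The interim is the only between-arm safety comparison specified before the end of the trial, and no independent board will read it. If an unremarkable result were recorded as showing that risk is not raised, the investigators would be drawing a conclusion that the data cannot carry. The type I error of the primary test is not at stake.

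**Working it through.** **Inputs.** From 2.9.1: 250 women in two equal groups, control cesarean rate 53%, a 33% relative reduction, two-sided α 0.05, 80% power, interim at 50%. From 2.9.2: p < 0.05. From section 1: 123 women in the earlier trial. The documents give no adverse event rates, so every rate below is assumed. Arm sizes for the earlier trial are not given either, so 61 v 62 is assumed.

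**The plan's own figure.** With p1 = 0.53, p2 = 0.53 × 0.67 = 0.3551 and p̄ = 0.44255:

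n per arm = [1.96√(2p̄(1−p̄)) + 0.842√(p1(1−p1) + p2(1−p2))]² / (p1−p2)² = 125.4, rounded up to 126, or 252 in total. The stated 250 is reproduced to within two women, and power at 125 per arm is 79.9%. Half of 250 is 125, about 62 v 63.

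**Power of the look, normal approximation.** Power = Φ{[|p1−p2| − 1.96√(2p̄(1−p̄)/n)] / √[(p1(1−p1)+p2(1−p2))/n]}. For 10% v 20%:

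- n = 62.5 per arm: (0.100 − 1.96 × 0.0639)/0.0632 = −0.40, power 34.5%.
- n = 61.5 per arm: (0.100 − 1.96 × 0.0644)/0.0638 = −0.41, power 34.1%.

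**Power by enumeration.** All tables were enumerated using chi-square, or Fisher's exact test if any expected count is below 5. Results are averaged over which arm has the higher rate.

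| Assumed rates | 62 v 63 | 61 v 62 |
|---|---|---|
| 5% v 10% | 13.8% | 13.6% |
| 10% v 20% | 34.7% | 34.9% |
| 15% v 30% | 52.6% | 52.8% |
| 20% v 40% | 69.4% | 69.4% |
| 25% v 50% | 83.1% | 82.7% |
| 10% v 29.5% | 80.5% | 80.1% |

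At equal event rates the interim and the earlier trial are equally sensitive. At the full 250 women, power for 10% v 20% is still only about 60%.

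**What particular results would show at 62 v 63** (no rates assumed):

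- 13/62 (21.0%) v 6/63 (9.5%): pooled rate 19/125 = 0.152, standard error √[0.152 × 0.848 × (1/62 + 1/63)] = 0.0642, z = 0.1144/0.0642 = 1.78, p = 0.075. One more event, 14/62 v 6/63, gives p = 0.046.
- Four events v none: p = 0.058 if the four are in the arm of 62, and 0.119 if in the arm of 63 (Fisher).
- Equal counts, 6/62 v 6/63: Newcombe 95% interval for the difference −10.9 to +11.3 points.
- No events in either arm: −5.7 to +5.8 points.

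**Reading the passages together.** The arithmetic shows an asymmetry. A large excess of a common event would be seen, but a null leaves a moderate excess open. That conflicts with 2.9.1 only if 2.9.1 says a null establishes equal risk. It says only that the look asks whether risk is increased in one arm. Asking that question is compatible with the hedged remark in section 1 that an absence of differences is probably due to size.

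**The case for a change.** The strongest case for a change is that the protocol has already treated such a null as reassurance. The 123-woman trial is the only evidence on chorioamnionitis under the combination cited in 2.8.1, since the reviews concern each method used alone. Section 2.8.2 then calls the risk comparable as part of the argument against a board. The same investigators will read the interim, with no stated rule for interpreting it, and a few sentences of caveat would cost almost nothing.

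Part of this stands. Section 1 and section 2.8.1 weigh the same trial differently, and a non-significant difference at 125 women is not evidence of equal risk.

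The rest is weaker:

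- That the interim null would be misread is a forecast; no passage says so.
- The equal-power comparison needs equal event rates. The earlier trial enrolled from 24 weeks and is not described as limited to nulliparous or obese women, whereas this protocol expects more obstetric complications in its population. Higher rates would raise power to detect a doubling.
- The no-board decision rests also on routine use and prior trials. Section 2.8.1 further cites evidence that tachysystole with fetal heart rate changes was less frequent when the balloon was added.
- Replacing the stated purpose with mere description would remove the plan's one commitment to judge whether harm is increased, which is a debatable exchange.

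**Conclusion.** No change to the plan follows. What remains is an uneven weighing of one earlier trial between the background and the safety rationale, and an interim purpose worded more firmly than 125 women can support if nothing is found. Neither alters the sample size, timing, outcomes, primary test or monitoring arrangements, and no stated figure is wrong.

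The limits of the look are those of any safety comparison at this size: about 14% power for 5% v 10%, 35% for 10% v 20%, 69% for 20% v 40%, and 80% only at about 10% v 29.5%. These rest on assumed rates, a 62 v 63 split and the general two-sided 0.05, which the plan does not expressly assign to the interim. Caveats in the text would not improve them. An analyst reporting the interim would ordinarily show counts and risk differences with 95% intervals by arm. An interval of about ±11 points around equal counts makes plain that equality has not been shown.

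### No by-arm tabulation is planned for adverse events outside the listed outcomes, although any adverse event is to be reported to the ethics committee

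*Combined protocol and SAP*

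**What the plan says.** Reporting is broad. Section 2.8.3 states: "Any adverse events will be reported to the Committee for the Protection of Human Subjects (CPHS"). It does not limit this to listed outcomes.

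Comparison between arms is narrower. Section 2.9.1 says "Interim analysis after 50% enrollment will be performed", and gives its purpose as "to determine if the risk of adverse events discussed in the secondary outcomes is increased in one arm relative to the other arm". For the final analysis, 2.9.2 says "Selected baseline characteristics and outcome measures will be compared" and then names the tests. It does not mention adverse events as a class.

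On oversight, 2.8.2 concludes that "the establishment of a safety data monitoring board is not necessary". It leaves safety to the principal investigator and a mentor, who "will monitor the progress of study and determine the safety parameters"; those parameters are not given.

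The listed outcomes are in 2.1.4 and 2.1.5. They include tachysystole needing intervention, clinical chorioamnionitis, a maternal morbidity composite (with endometritis, transfusion, ICU admission and death), NICU admission, neonatal sepsis and a neonatal composite. Neither section has a general adverse-event outcome.

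**The concern.** The trial intends to collect reports of any adverse event, but the plan uses only part of them when it compares the arms. An event that is not on the list goes to the committee as a single case. Single cases do not show an imbalance; that needs counts over the number randomized to each arm.

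This matters more than usual here because there is no monitoring board and the investigators' safety parameters are unspecified. The 50% look is therefore the only by-arm harm check that the plan states before the end of the trial. The background section also says that the combination has not been prospectively compared with misoprostol alone in women with BMI of 30 or more. A fixed list drawn from earlier experience is weakest for harms that were not foreseen. At stake is the completeness of the safety conclusion, not the cesarean result.

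**Working it through.** **1. The sections side by side**

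| Step | Section | Scope | By arm? |
|---|---|---|---|
| Reporting to CPHS | 2.8.3 | Any adverse event | Not stated |
| Oversight by investigator and mentor | 2.8.2 | Parameters not given | Not stated |
| Interim look | 2.9.1 | Adverse events among the secondary outcomes | Yes |
| Final analysis | 2.9.2 | Selected baseline characteristics and outcome measures | Yes |

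Both by-arm rows are tied to the outcome list, and the one row that covers every event has no by-arm step. An unlisted event therefore reaches no planned arm comparison. In 2.9.1 this follows from a stated restriction, not from silence alone.

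**2. What the list does cover**

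Section 2.8.1 discusses one possible balloon risk, chorioamnionitis, and 2.1.4 lists it. Endometritis is in the maternal composite. Only events outside 2.1.4 and 2.1.5 fall into the gap.

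**3. Arm sizes**

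The plan's 125 per group can be reproduced. With p1 = 0.53, p2 = 0.53 × 0.67 = 0.3551, mean p = 0.44255, two-sided alpha 0.05 and 80% power:

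n = [1.96 × √(2 × 0.44255 × 0.55745) + 0.8416 × √(0.53 × 0.47 + 0.3551 × 0.6449)]² / (0.53 − 0.3551)² ≈ 3.836 / 0.03059 ≈ 125.4

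That rounds up to 126 per arm, against 125 stated; power at 125 is 79.9%. The concern does not rest on this figure. It only fixes the denominators: 125 per arm at the end and about 62 per arm at the 50% look.

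**4. Would unlisted events turn up at all?**

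The documents give no rates, so a range is assumed for an event that occurs in one arm only. Expected count = r × n; chance of at least one case = 1 − (1 − r)^n.

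| Assumed rate r | Expected, n = 62 | At least one | Expected, n = 125 | At least one |
|---|---|---|---|---|
| 1% | 0.62 | 46.4% | 1.25 | 71.5% |
| 2% | 1.24 | 71.4% | 2.5 | 92.0% |
| 4% | 2.48 | 92.0% | 5 | 99.4% |
| 5% | 3.1 | 95.8% | 6.25 | 99.8% |

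Across most of this range such events would probably occur and be reported.

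**5. What could a by-arm table show?**

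If all k events fall in one of two equal arms of n, the two-sided Fisher p is 2 × [n(n−1)…(n−k+1)] / [2n(2n−1)…(2n−k+1)].

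- 5 v 0 of 125 per arm: 2 × (125 × 124 × 123 × 122 × 121) / (250 × 249 × 248 × 247 × 246) ≈ 2 × 0.0300 = 0.06.
- 3 v 0 of 62 per arm: 2 × (62 × 61 × 60) / (124 × 123 × 122) ≈ 0.24.
- 2 v 0 of 62 per arm: 2 × (62 × 61) / (124 × 123) ≈ 0.50.

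The power of Fisher's exact test for assumed rates of 1% v 5% is about 5% at the look and 30% at the end; for 2% v 10% it is about 29% and 70%. A formal test would mostly miss such differences. A descriptive table is the right tool, and an imbalance in it is a signal for review, not proof.

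**The case against.** The strongest reply is that the plan does not forbid a wider comparison. The trial is open-label, so the arm behind each report is known, and the investigator and mentor could review all events by arm under 2.8.2. This stands in part: the claim must be that no comparison is planned, not that none could take place. It does not close the gap, because 2.9.1 states the narrower scope and 2.8.2 commits to nothing specific.

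A second reply is that the list already catches most serious harm. This also stands. A severe consequence of a complication could appear as transfusion, ICU admission, sepsis or death, all of which are listed, and 2.8.2 describes both interventions as routine care.

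Three stronger readings are tempting, and the documents do not support them.

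- A reader might infer that balloon harms as a whole go uncompared. Chorioamnionitis and endometritis are listed, and no specific unlisted balloon harm is named.
- A reader might treat failed placement as an uncompared harm, since 2.7 provides for the case "If the Foley is unable to be placed". Failed placement can occur only in Group 1, so there is nothing to compare it with, and no section calls it an adverse event.
- A reader might take the balloon to be the only difference between arms. Section 2.8.1 expects fewer misoprostol doses when the balloon is added, so drug exposure may differ too; tachysystole, the related harm, is listed.

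**Conclusion.** The point holds in a limited form. Any adverse event is reported, but both planned arm comparisons are confined to listed outcomes, so unlisted events have no planned by-arm tabulation and no board to ask for one. It does not change the cesarean analysis, the sample size or any test. What it affects is how complete the safety comparison is, and it is worth correcting because the correction costs little.

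Its size cannot be read from the documents. With assumed rates of 1% to 5% in one arm, at least one case would be seen by the end with probability 71.5% to 99.8%, yet even 5 v 0 would give a p of only about 0.06. The conclusion assumes that 2.8.3 is followed as written and that the word selected in 2.9.2 does not drop any listed harm. If it does, the final comparison is narrower still.

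**What to change.** In 2.9.1 and 2.9.2, state that all adverse events reported under 2.8.3, listed or not, will be tabulated by randomized arm at the 50% look and in the final report. Give the number of women with an event and the number of events, over the number randomized to each arm, descriptively and without tests. State that an imbalance prompts review and is not taken as proof of harm.

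Failed or repeated balloon placement may be reported separately as a one-arm count for Group 1, not as an arm comparison.

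The cost is one extra descriptive table at each of two analyses that are already planned. One form field may also be needed: 2.7 has a research nurse collecting data on the course of labor, but does not say whether placement failure is recorded. Enrollment, alpha and the treatment of participants do not change.
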